6.4.2. Efficacy Assessments

6.4.2.1. Mayo score

The total, adapted, and partial Mayo scores and the Patient-Reported Outcome 2 (PRO2) score will be assessed as specified in Schedule of Study Procedures ([Table 1](#), [Table 2](#), and [Table 3](#)). These scores are comprised of:

- The total Mayo score (0-12 points with 12 reflecting the highest severity) is comprised of four subscores: rectal bleeding (0 - 3), stool frequency (0 - 3), physician's global assessment (0 -3), and Mayo endoscopic subscore (0 – 3).
- The Partial Mayo score (0-9) is comprised of the first three Mayo subscores without the endoscopic subscore.
- The Adapted Mayo score (0-9) is comprised of the rectal bleeding, stool frequency, and endoscopic subscore (i.e., total Mayo score but without the PGA).
- The PRO-2 score (0-6 points with 6 reflecting the highest severity) is comprised of two subscores: rectal bleeding (0 - 3), stool frequency (0 - 3) subscores.

The stool frequency subscore of each day is the number of bowel movements exceeding the normal frequency (before onset of symptoms from UC or when subject is not in a flare, whichever is lower) and will be averaged over the last 3 days (which may or may not be consecutive) for which symptom data are available during the week prior to each Study visit; the rectal bleeding subscore reflects the worst bleeding of each day and will also be averaged over the last 3 days (which may or may not be consecutive) for which symptom data are available during the week prior to each Study visit. Note that symptoms on the day of an oral bowel preparation, the day of an endoscopy, and the day following an endoscopy should be excluded in any symptom score calculation to avoid diarrhea and/or rectal bleeding from the bowel preparation or the endoscopy or the biopsy. Refer to [Appendix 3](#) for further details. It is ideal, if possible, that the physician global assessment of each visit is completed by the same investigator of each subject. Of note, endoscopic subscore of 1 requires absence of friability.

[REDACTED]

[REDACTED]

[REDACTED]

[REDACTED]

[REDACTED]

[REDACTED]

[REDACTED]

[REDACTED]

[REDACTED]

[REDACTED]

[REDACTED]

[REDACTED]

[REDACTED]

[REDACTED]

[REDACTED]

[REDACTED]

[REDACTED]

[REDACTED]

- [REDACTED]
- [REDACTED]
- [REDACTED]
- [REDACTED]

[REDACTED]

[REDACTED]

[REDACTED]

6.4.2.6.5. Subject Diary

Subjects are required to enter diary data continuously throughout each Study (from Screening Stage 1 to last visit on study). Subjects will be provided an electronic diary at the Screening Stage 1 visit and will be required to bring the Study diary to each of their Study visits. Diary data will be reviewed and collected at the site at each Study visit until the last visit of each Study.

Subjects will report on a daily basis items including the following:

- Total stool frequency over the preceding 24-hour period
- Presence and description of blood in the stools (if any): none, streak of blood <50% of stools, obvious blood with $\geq 50\%$ of stools, or blood alone without stool
- Time (hour and minute) of Study drug administration (should be in the morning)

The information extracted will be used for calculation of the clinical scores. Symptoms on the day of and the day after any endoscopic procedure will not be used to calculate the clinical scores in order to avoid confounding effects from bowel preparation-related altered bowel frequency and/or rectal bleeding from the biopsies. On days where subject takes an oral bowel preparation for an endoscopic procedure, the symptoms on the day of the bowel preparation are also not counted to avoid confounding effects from the prep.

6.4.3. Pharmacokinetic and Pharmacodynamics Assessments

A sparse PK sampling strategy is being employed in this Study where random samples will be taken at select Study visits both immediately prior to treatment with Study drug and during treatment with Study drug; time of Study drug ingestion needs to be carefully documented the day before and the day of each Study visit where PK samples will be collected.

Disease-related surrogate markers (e.g., [REDACTED]) will be assessed. Other disease-related biomarkers may be assessed.

Whole blood, serum, and plasma samples will be collected and stored for potential future additional biomarker profiling.

6.4.4. Safety Assessments

Subject safety will be assessed throughout the Study using standard measures, including vital signs, 12-lead ECGs, blood and urine safety laboratory tests, physical examinations, concomitant medication usage, and adverse event (AE) monitoring. These will be collected from all subjects at visits as indicated in [Table 1](#), [Table 2](#), and [Table 3](#).

6.4.4.1. Adverse Events

Refer to Section [6.4.1.13](#)

6.4.4.2. Medical History

Refer to Section [6.4.1.3](#)

6.4.4.3. Physical Examination

Refer to Section [6.4.1.9](#)

6.4.4.4. Vital Signs

Refer to Section [6.4.1.7](#)

6.4.4.5. Laboratory Tests

Refer to Section [6.4.1](#)

6.5. Concomitant Medications

Refer to Section [6.4.1.12](#)

6.5.1. Prohibited Medications

Immunomodifying agents (Refer to [Appendix 6](#)) are prohibited until the End of Study visit. The use of any prohibited UC Medication would result in subject discontinuation as defined in Section [6.6.1](#), except for the use of rectal aminosalicylates or rectal corticosteroids for clinical management during clinical flare assessment (during the Maintenance Study) if there is a contraindication for oral corticosteroids (see Section [6.5.2](#)).

The use of the following medications, which may confound the safety evaluation of the Study, are prohibited:

- Any prescription drugs started or which had a dose adjustment within the 28 days prior to Day 1 until the day of the last dose (with the exception of hormonal contraceptives, hormone replacement therapy, vitamin D, insulin therapy, iron, corticosteroid [see below], and replacement thyroid hormone) unless deemed by the investigator to be medically necessary and unlikely to confound the efficacy assessment of Study drug. New medications that may confound the efficacy assessment may be considered with Sponsor approval on an individual basis.
- Any initiation or dose adjustment of over-the-counter medications including herbals, vitamins, or supplements within 14 days prior to Day 1 until the day of the last Study dose, unless deemed unlikely to confound safety assessment of Study drug by the investigator. New medications that may confound the efficacy assessment may be considered with Sponsor approval on an individual basis.
- Strong P-gp, BCRP and/or CYP3A4 inhibitors and inducers. This exclusion applies to concomitant medications, herbal supplements and ordinary dietary intake. The package insert, FDA website, and clinical judgment may be used to assess the potential of concomitant medications to interact with Study Drug. Refer to [Appendix 6 Prohibited Medications](#). For clarity:
 - Any amount of grapefruit in the diet is prohibited;
 - Curcumin is prohibited as a concentrated supplement, but dietary intake is allowed;
 - Corticosteroids at doses not excluded elsewhere in the protocol are not considered strong CYP3A4/P-gp/BCRP inducers.
- Subject must avoid live viral vaccines (e.g., MMR, varicella zoster, herpes zoster, oral polio virus, FluMist[®], attenuated typhoid fever vaccine, attenuated rotavirus vaccine, yellow fever vaccine, or any investigational live vaccine) during the Study and for 8 weeks following completion of the Study. Subject must be willing to avoid close contact with any household member who has been vaccinated with a live attenuated vaccine within 2 weeks after vaccination.

6.5.2. Permitted Medications

Permitted medications include, but are not limited to:

- Oral corticosteroids for UC are allowed during either the Phase 2b or the Phase 3 Induction Study but need to stay at a stable dose until Week 8. Note that steroid tapering during Induction is discouraged unless medically necessary. During extended induction, the subjects may, but are not required to, taper corticosteroids according to the regimen suggested below in Section 6.5.3. Reductions or increases in doses during the Maintenance Study are permitted as defined in Section 6.5.3. Corticosteroids are permitted rescue medications.

- Oral corticosteroids for non-UC indications are allowed, if medically necessary, after discussion with the Sponsor. The dose should, but does not need to, be tapered as outlined in Section 6.5.3.
- Doses of oral aminosalicylate, probiotics, or antibiotics prescribed for UC should be stable during the Phase 2b Induction/Phase 3 Induction Studies and Phase 3 Maintenance Study. However, they can be discontinued or undergo dose adjustment if the investigator deems their use has resulted in adverse effects. Oral aminosalicylates are also permitted rescue medications.
- Rectal aminosalicylates or rectal corticosteroids for clinical management during clinical flare assessment (during the Maintenance Study) if there is a contraindication for oral corticosteroids. If these are to be used, the best effort should be made to taper or stop these as soon as possible and before mWeek 40, if possible.
- Anti-diarrheal agents, which can be tapered or stopped if symptoms are improved during the Study; however, it is encouraged to continue at the same dose of anti-diarrheal medications throughout all studies. The addition of anti-diarrheal agents, although allowed, should be discouraged during the study if subject was not on an anti-diarrheal agent upon enrollment into the Induction Study.
- Sedating medications for endoscopy are permitted
- Antibiotics for infections
- Addition of, cessation of, or dose adjustments for the following are allowed during Screening or any other time during the study:
 - a. Hormonal therapy for post-menopausal females
 - b. Oral contraception for women of child-bearing potential
 - c. NSAIDs taken on a regular (≤ 3 times per week, on average) basis
 - d. Aspirin for cardioprotection is permitted at a maximum dose of 325 mg/day
 - e. Vitamin D
 - f. Insulin therapy
 - g. Replacement thyroid hormone,
 - h. Iron, if investigator deems this is medically indicated

6.5.3. Corticosteroid Tapering

- Oral corticosteroids are permitted at a stable dose ≤ 25 mg/day of prednisone or beclomethasone dipropionate (ie, Clipper) at ≤ 5 mg/day or equivalent or ≤ 9 mg/day budesonide during Induction Studies (Weeks 1-8).
- During Extended Induction, the Investigator may taper corticosteroids if he or she feels it is indicated, using the tapering regimen for the Maintenance Study described below.
- Upon entering the Phase 3 Maintenance Study (mWeek 0), subjects must start tapering their corticosteroid dose **OR** where corticosteroids have been used as rescue

medications, tapering must begin 2 weeks after an increase in corticosteroid therapy, using the regimen outlined below:

- Prednisone (or equivalent) dose should be tapered by 5 mg/day every week until 10 mg/day (or prednisone equivalent) and then by 2.5 mg/day every week (or prednisone equivalent) until completely off.
- If subject is on budesonide or beclomethasone, then the dose should be tapered according to local clinical practice.
- If subject is on corticosteroids as a rescue medication during the Maintenance Study, the dose may be tapered as outlined above or more quickly than recommended above. It is recommended, but not required, to start tapering the corticosteroid dose within 2 weeks after initiation or dose increase.

6.5.4. Rescue Medications During Maintenance Study

Subjects meeting loss of response definition during the Maintenance Study may initiate permitted rescue medications, which consist of corticosteroids and aminosalicylates.

- An increase up to the Induction Study Day 1 corticosteroid or aminosalicylate dose is allowed as often as clinically indicated and subject can still stay on study drug.
- Certain increases above the Maintenance Study Week 0 (which should be the same as Induction Study Day 1, in most cases) corticosteroid dose or initiation of corticosteroid without subject having been on corticosteroid upon Induction Study enrollment is allowed, and the subject should remain on study drug, but may lead to the subject meeting criteria for treatment failure (further defined in the statistical analysis plan).
- Increases above baseline (the Maintenance Study Week 0, which should be the same as Induction Study Day 1) or new initiation of aminosalicylates are permitted but may lead to the subject meeting criteria for treatment failure (further defined in the statistical analysis plan).

6.5.5. Restrictions on Alcohol Consumption and Illicit Drug Use

Alcohol abuse or illicit drug abuse, per the judgment of the investigator, within 1 year of Screening until the EOS visit is not allowed.

6.6. Discontinuation

6.6.1. Subject Discontinuation

Any subject may withdraw their consent to participate in the Study at any time without prejudice. The investigator must withdraw from the Study any subject who requests to be withdrawn. A subject's participation in the Study may be discontinued at any time at the discretion of the investigator and in accordance with his or her clinical judgment. Subjects must also be discontinued on study drug for any AESI (except non-melanoma skin cancer, mono-dermatomal

herpes zoster, and certain laboratory abnormalities that are deemed by the investigator to not place subjects at immediate safety risk) or if the subject becomes pregnant. When possible, the tests and evaluations listed for the termination visit should be carried out. If a subject withdraws before completing the Study, the reason for withdrawal is to be documented on the CRF.

The Sponsor will be notified of all subject withdrawals.

Reasons for which the investigator or the Sponsor may withdraw a subject from the Phase 2b/Phase 3 Induction Studies or Phase 3 Maintenance Study or a subject may choose to terminate participation before completion include the following:

- Adverse event
- Subject choice/Withdrawal of consent
- Major violation of the protocol
- Termination of the Study by the Sponsor
- Initiation of a prohibited medication ([Appendix 6](#)) for UC (except for rectal aminosalicylates and rectal corticosteroids during the clinical flare assessment)
- Lost to follow-up
- Pregnancy
- Colectomy

Subjects with laboratory abnormalities as outlined in Section 7.2 (i.e., two sequential occurrences of renal, leukocyte, leukocyte subset, or hepatic panel abnormalities or hepatic panel abnormalities with clinical sign or symptom of acute liver failure) should discontinue the study drug. Any non-laboratory-related AE considered an AESI defined in Section 7.1.4, except for non-melanoma skin cancer and mono-dermatomal herpes zoster, should also lead to study drug discontinuation. Subjects who discontinue Study drug early because of an adverse reaction should be encouraged to continue their participation in the follow-up safety assessments. If a subject fails to return for scheduled visits, a documented effort must be made to determine the reason.

Subject study completion is defined as completing the last study visit whether or not the subject discontinued study drug prematurely.

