7.1.4. Adverse Events of Special Interest (AESI)

At each Study visit, the Investigator (or designee) will specifically query for any adverse events of special interest (AESI). The following events are considered AESIs for this Study:

- Suspected or confirmed intestinal perforation
- Complicated herpes zoster (multi-dermatomal, disseminated, or with ophthalmic or CNS involvement)
- Malignancy excluding non-melanoma skin cancer
- Non-melanoma skin cancer
- Serious infection (e.g., that requires hospitalization or intravenous antibiotics)
- Opportunistic infections
- Thromboembolic disease (e.g., DVT, pulmonary embolism)
- Clinical laboratory abnormalities of concern (Refer to Section 7.2)
- Major cardiovascular event (e.g., myocardial infarction or cerebrovascular accident)

All AESIs, except for non-melanoma skin cancers and mono-dermatomal herpes zoster, must be reported to TBPH Clinical Safety and Pharmacovigilance within 24 hours of the time the Investigator or his/her designee becomes aware of an AESI (Refer to Section 7.4.3). Except for non-melanoma skin cancer that has been fully resected, mono-dermatomal herpes zoster, and certain laboratory abnormalities that are deemed by the investigator to not place subjects at immediate safety risk, all of these AESI’s should lead to discontinuation of the study drug. For each of these AESI, an additional targeted questionnaire needs to be completed to assess for risk factors. For thromboembolic events in particular, the subject should undergo evaluation for hypercoagulable state (e.g., with clinically relevant investigations, such as referral to a specialist and/or blood testing for a predisposition to a hypercoagulable state) and repeat imaging to assess resolution of the finding.

Besides these AESI, for other AEs, study drug may be interrupted and resumed as deemed medically appropriate by the investigator (e.g. during an infection that requires oral antimicrobial treatment).

7.2. Clinical Laboratory Abnormalities and Other Abnormal Assessments as Adverse Events or Serious Adverse Events

Abnormal laboratory findings (such as clinical chemistry, hematology, or urinalysis) or other abnormal assessments (such as electrocardiograms [ECGs], X-rays, or vital signs) that are associated with signs and/or symptoms or are considered clinically significant in the judgment of the investigator must be recorded as AEs or SAEs if they meet the definition of an adverse event

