1. INTRODUCTION

This document outlines the plan for the summarization and analysis of clinical data collected in the Phase 3 Maintenance Study of Protocol 0157 for TD-1473.

Protocol 0157 comprises 3 separate studies within a single protocol. The purpose of multiple studies within a single protocol is to increase operational efficiency and reduce operational costs.

The 0157 maintenance study was terminated early due to lack of efficacy in the 0157 Phase 2b Induction study, all subjects date of last dose occurred by 11 September 2021 date and end of study visit by 20 October 2021 date.

The 0157 CSR will be an abbreviated CSR incorporating data from the Phase 2b Induction and Phase 3 Maintenance study and as a result all protocol defined analyses will not be performed.

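### Protocol Sections 6.6.1 and 7.1.4 give different study drug discontinuation rules for a non-melanoma skin cancer that is not fully resected

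*Protocol*

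**What the plan says.** The protocol states the stopping rule for adverse events of special interest (AESIs) three times.

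- Section 6.6.1, first statement: "Subjects must also be discontinued on study drug for any AESI (except non-melanoma skin cancer". The bracket goes on to except mono-dermatomal herpes zoster and certain laboratory abnormalities. Nothing is said about resection.
- Section 6.6.1, second statement, on AESIs other than laboratory findings: "except for non-melanoma skin cancer and mono-dermatomal herpes zoster, should also lead to study drug discontinuation". It cites Section 7.1.4 for the definition of an AESI. Again there is no resection condition.
- Section 7.1.4, after the list of AESIs, which includes non-melanoma skin cancer: "Except for non-melanoma skin cancer that has been fully resected", together with the same two other exceptions, all of these events "should lead to discontinuation of the study drug".

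Three further provisions bear on how the rule works in practice. Section 6.6.1 says that a subject's "participation in the Study may be discontinued at any time at the discretion of the investigator". Section 7.1.4 says that for each of these AESIs "an additional targeted questionnaire needs to be completed to assess for risk factors". It also has a pause-and-restart provision: "Besides these AESI, for other AEs, study drug may be interrupted and resumed as deemed medically appropriate by the investigator".

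**The concern.** A rule for stopping study drug on safety grounds should give one answer for one event. Here the answer for a non-melanoma skin cancer that is not fully resected depends on which section the site has open. Section 6.6.1 is headed as the section on subject discontinuation, so it is a natural place to look. A site that reads only that section finds the event listed as an exception and could keep the subject on a JAK inhibitor, although 7.1.4 says the event should lead to stopping.

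What is at stake is consistent handling of a small number of subjects across sites. No efficacy conclusion depends on it.

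**Working it through.** No arithmetic applies. The check is to set the three statements side by side for the two possible states of the lesion.

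| State of the lesion | 6.6.1, first statement (must) | 6.6.1, second statement (should) | 7.1.4 (should) |
|---|---|---|---|
| Fully resected | excepted | excepted | excepted |
| Not fully resected | excepted | excepted | discontinue |

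The first row agrees throughout. The second does not: two of the three statements except the lesion and one calls for discontinuation.

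Next, could any other text bring the second row into line?

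1. *The cross-reference in 6.6.1.* The second statement points to 7.1.4 for which events count as AESIs. It then states its own exception without a condition, so the resection condition is not carried over. The first statement has no reference to 7.1.4 at all.
2. *The qualifier about immediate safety risk in the first statement.* It reads as attached to the laboratory abnormalities and says nothing about resection.
3. *Pausing and restarting.* The sentence in 7.1.4 is worded for adverse events other than these AESIs. It therefore does not soften the 7.1.4 instruction for a lesion not fully resected.
4. *The other skin cancer exception in 7.1.4.* Section 7.1.4 also has an exception for non-melanoma skin cancer with no resection condition, but that one concerns 24-hour reporting. It does not concern study drug.
5. *Investigator discretion in 6.6.1.* It permits stopping. It does not supply the instruction to stop that 7.1.4 gives.

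The difference therefore stands. It lies in current body text that is not redacted at these places.

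Finally, the data side. Section 7.1.4 has AESIs queried at each visit, Section 7.4.2 has all adverse events recorded on the CRF, and Section 3.7.2.1 of both the Phase 2b SAP and the Maintenance SAP summarises AESIs. None of this depends on whether study drug is stopped. AESI data stay complete under either rule, and no sample size, power or type I error figure uses the rule.

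**The case against.** The strongest reply is that the two sections can be followed together. The first 6.6.1 statement is a mandatory rule with exceptions, and falling outside a mandatory rule is not an order to continue. A site that stops drug under 7.1.4 breaches nothing in 6.6.1, which allows discontinuation on clinical judgment and lists an adverse event among the reasons for withdrawal. A site that looks up what an AESI is will open 7.1.4, where the stricter text comes shortly after the list, followed by the questionnaire requirement.

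Much of this stands. A reader might infer that 6.6.1 instructs sites to keep dosing such a subject; it does not. The clearest mismatch is between the second 6.6.1 statement and 7.1.4, since both are phrased as *should* and reach different answers. What the reply does not do is remove the difference: discretion and proximity make the wrong outcome less likely, but 6.6.1 read alone still lists the event as an exception.

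A second reply concerns the remedy. Writing the resection condition into the first 6.6.1 statement would turn the *should* of 7.1.4 into a *must* for this event. Neither section says when resection is judged, and a newly diagnosed lesion may simply be waiting for excision. Read literally, such a subject would have to stop study drug. This reply stands in full and shapes the fix.

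**Conclusion.** The inconsistency is real and minor. For a non-melanoma skin cancer not fully resected, both statements in 6.6.1 except the event from discontinuation and 7.1.4 does not.

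Its size is limited in three ways. Only subjects with such a lesion are affected; the documents give no expected number, and that it is small is a judgment. Planned dosing ran to at most 60 weeks (Synopsis). The Maintenance Study was then terminated early, and its SAP states that "all subjects date of last dose occurred by 11 September 2021", which limits exposure further.

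Two stronger readings are tempting and are not supported. One is that 6.6.1 is the erroneous section and 7.1.4 the intended rule. The documents do not say which was intended. Exclusion criterion 26 accepts a prior basal or squamous cell skin carcinoma only if completely resected and free of recurrence for at least 1 year. That fits the condition in 7.1.4 and favours the more cautious rule, but it governs entry and does not settle intent for events on treatment. The other is that the discrepancy compromises the safety data or the trial's conclusions. It does neither, for the reasons in the check above.

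The verdict assumes that a site may act on 6.6.1 without consulting 7.1.4. That is plausible, but nothing in the documents shows that it happened.

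**What to change.** Adopt the more cautious rule that the protocol already contains, with two small changes in Section 6.6.1.

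- *Second statement:* after non-melanoma skin cancer insert *that has been fully resected*, and after mono-dermatomal herpes zoster insert *(see Section 7.1.4)*. This matches 7.1.4 in content and in strength, since both say *should*.
- *First statement:* keep the exception, but after non-melanoma skin cancer insert *(handled per Section 7.1.4)*. The event stays outside the mandatory rule, so a lesion awaiting excision is not forced into discontinuation, and the reader is sent to the one place where the condition is stated.

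The rest of both sentences, including *must* for the AESIs not excepted and the pregnancy rule, stays as it is. If the sponsor in fact intended the broader exception, the alternative is to delete the resection condition from 7.1.4; either way the sections should agree.

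The cost is protocol wording in two sentences. Data collection, analysis and sample size do not change.

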(or serious adverse event), as described in Section 7.1.1 (Adverse Event) and Section 7.1.2 (Serious Adverse Event).

Clinical laboratory abnormalities of concern may include, but are not limited to, the following where the investigator must recheck within 2-7 days, except for AST or ALT > 3x ULN where these need to be rechecked within 48-72 hours, as deemed appropriate by the investigator:

- clinically significant reduction in neutrophils or leukocytes or lymphocytes that may place subjects at higher risk for infection such as:
 - moderate or severe neutropenia (e.g., absolute neutrophil count of $< 1.0 \times 10^9/L$)
 - moderate or severe leukopenia (e.g., white blood cell count of $< 2.0 \times 10^9/L$)
 - moderate or severe lymphocytopenia (e.g., absolute lymphocyte count of $< 0.5 \times 10^9/L$)
- abnormal hepatic panel (AST or ALT > 3x ULN)
- an excessive decrease in creatinine clearance (e.g., a reduction by $\geq 50\%$ from baseline (baseline for this purpose is defined as creatinine clearance calculated for Day 1, predose activities))

Depending on the subject's baseline and individual scenario, the investigator should report as an AESI and stop study drug treatment if any of the below is seen:

- moderate or severe neutropenia (e.g., absolute neutrophil count of $< 1.0 \times 10^9/L$) on two sequential laboratory reports
- moderate or severe leukopenia (e.g., white blood cell count of $< 2.0 \times 10^9/L$) on two sequential laboratory reports
- moderate or severe lymphocytopenia (e.g., absolute lymphocyte count of $< 0.5 \times 10^9/L$) on two sequential laboratory reports
- a reduction by $\geq 50\%$ from baseline in creatinine clearance on two sequential laboratory reports
- Abnormal AST or ALT > 3x ULN on two sequential laboratory reports with bilirubin > 2x ULN on at least one of the two laboratory reports or international normalized ratio (INR) > 1.5 on at least one of the two reports (INR will be checked locally)
- AST or ALT > 5x ULN on two sequential laboratory reports at least 2 weeks apart
- AST or ALT > 3x ULN associated with signs or symptoms suggestive of acute liver injury (e.g., the appearance of fatigue, nausea, vomiting, right upper quadrant pain or tenderness, fever, rash, and/or eosinophilia [$> 5\%$])
- AST or ALT > 8x ULN on one laboratory report

Note: See [Appendix 10](#) for an algorithm of evaluating and managing subjects with ALT or AST > 3x ULN.

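### The liver stopping criteria restated in Protocol Section 6.6.1 do not match the Section 7.2 list they claim to summarise

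*Protocol*

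**What the plan says.** Protocol Section 6.6.1 begins its laboratory rule with a pointer: "Subjects with laboratory abnormalities as outlined in Section 7.2" should come off study drug. A parenthesis introduced by i.e. then restates the rule in two parts:

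- "two sequential occurrences of renal, leukocyte, leukocyte subset, or hepatic panel abnormalities";
- "hepatic panel abnormalities with clinical sign or symptom of acute liver failure".

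Earlier in the same section, any adverse event of special interest (AESI) is also a reason to stop. Among the exceptions are certain laboratory abnormalities that the investigator judges not to pose an immediate safety risk.

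Protocol Section 7.2 has two lists. The first names abnormalities to be rechecked and includes "abnormal hepatic panel (AST or ALT > 3x ULN"; for that item the recheck is due within 48 to 72 hours. The second is the stop list. After a preface that leaves room for the subject's baseline and circumstances, it says "the investigator should report as an AESI and stop study drug treatment if any of the below is seen". Its four liver items are:

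1. "Abnormal AST or ALT > 3x ULN on two sequential laboratory reports with bilirubin > 2x ULN on at least one of the two" reports, or INR above 1.5 on at least one of them;
2. AST or ALT above 5x ULN on two sequential reports separated by 2 weeks or more;
3. AST or ALT above 3x ULN with signs or symptoms pointing to acute liver injury;
4. "AST or ALT > 8x ULN on one laboratory report".

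Section 7.2 then refers to Appendix 10 for an algorithm covering ALT or AST above 3x ULN. The algorithm figure is not in the supplied text.

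**The concern.** A parenthesis introduced by i.e. should say the same thing as its source. For the liver it does not: the bilirubin or INR condition, the 5x level, the 2-week spacing and the single-report 8x item are all absent, and acute liver injury has become acute liver failure. A site working from 6.6.1 and a site working from 7.2 could treat the same result differently.

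This is first a safety-conduct matter, but it also reaches the analysis. Both SAPs tabulate adverse events leading to discontinuation of study drug (Section 3.7.2 in each). In the Phase 2b SAP, stopping for a liver abnormality falls under intercurrent event 7 (Section 3.3.4.1). For the key secondary endpoint, that event sets the Week 8 status to not in remission (Sections 3.4.4.1 and 3.4.4.2). If the stopping rule varies by the section read, discontinuation counts and some remission statuses vary with it.

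**Working it through.** No power, alpha or sample size is involved and the plan gives no figure to reproduce. The check applies each text, as written, to the same liver results. The only input taken from one section into the other is the meaning of an abnormal hepatic panel: AST or ALT above 3x ULN, from 7.2, the section that 6.6.1 cites.

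**Item by item**

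| Element | 6.6.1 parenthesis | 7.2 stop list |
|---|---|---|
| Neutrophils, leukocytes, lymphocytes, creatinine clearance | two sequential occurrences | two sequential reports |
| Two sequential values > 3x ULN | sufficient alone | needs bilirubin > 2x ULN or INR > 1.5 |
| Two sequential values > 5x ULN | no separate item | needs spacing of 2 weeks or more |
| > 3x ULN with clinical signs | acute liver failure | acute liver injury |
| One value > 8x ULN | absent | sufficient alone |

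The four non-liver items agree. All the differences are in the liver rows.

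**Same result under each text**

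- **A. ALT 4x ULN on two sequential reports, bilirubin and INR normal, no symptoms.** 6.6.1: 4 > 3 twice, so stop. 7.2: item 1 fails (no bilirubin or INR elevation), item 2 fails (4 is not > 5), item 3 fails (no symptoms), item 4 fails (4 is not > 8). No stop criterion is met.
- **B. ALT 6x ULN on two reports 3 days apart, otherwise as A.** 6.6.1: stop. 7.2: 6 > 5, but 3 days is less than 14, so item 2 is not yet met; items 1, 3 and 4 also fail. The 48 to 72 hour recheck (2 to 3 days) makes this spacing the expected one.
- **C. ALT 9x ULN on one report, no symptoms.** 7.2: 9 > 8, so stop. The 6.6.1 parenthesis is not met, but 7.2 makes the result an AESI, and the general AESI sentence in 6.6.1 then calls for stopping, subject to the investigator exception.
- **D. ALT 4x ULN once, with fatigue and nausea suggesting liver injury but not failure.** 7.2: item 3, stop. 6.6.1: reached only through the AESI sentence, as in C.
- **E. ALT 4x ULN on two sequential reports with bilirubin > 2x ULN.** Both texts: stop.

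**Redundancy check.** Every pair of reports that meets 7.2 item 1 or item 2 already has two sequential values above 3x. If the literal 6.6.1 text governed, the bilirubin or INR condition, the 5x level and the 2-week spacing would have no effect on stopping. The two texts therefore cannot both describe the intended rule for two-report cases.

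**The case against.** The strongest reply is that 6.6.1 is a pointer and not a second rule. Its parenthesis gives no multiple of ULN, so a site must open 7.2 to apply it and will find an explicit stop list there. Read as a loose gloss on that list, the parenthesis makes case A a non-stop in both sections. This is a possible reading, but it does not remove the problem. The hepatic panel is a term 7.2 itself uses and defines, in its recheck list. The parenthesis also matches 7.2 for the leukocyte and renal items, so a site has reason to take the hepatic part literally as well.

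Four stronger readings are tempting, and the documents do not support them:

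- **The same result must lead to stopping under one section and continuing under the other.** Section 7.2 never says to continue. It does not list cases A and B for stopping, its preface allows judgment, and 6.6.1 lets the investigator discontinue a subject at any time.
- **A single value of 9x ULN falls outside 6.6.1.** It falls outside the parenthesis only; the AESI sentence reaches it, with the exception noted.
- **AESI counts depend on the 6.6.1 wording.** AESIs are defined in 7.1.4 and 7.2. The parenthesis governs stopping and does not define them.
- **Liver toxicity is an expected risk of this drug.** Protocol Section 1.5 reports liver test changes for tofacitinib, a systemic JAK inhibitor, and anticipates minimal risk in this study.

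The reply also stands on one further point: the missing Appendix 10 algorithm may address case A, so what sites actually did cannot be inferred.

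**Conclusion.** The point holds as a mismatch between a restatement and its source, limited to the liver criteria. Cases A and B show it most clearly: the literal 6.6.1 text calls for stopping and no 7.2 stop criterion is met. For cases C and D the gap is in the parenthesis alone.

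The conclusion rests on taking the hepatic panel term as 7.2 defines it and on reading the i.e. text literally. The documents give no rate of such results by which to size the effect on discontinuation tables or on the key secondary endpoint. The endpoint effect is confined to subjects who stop before Week 8 and would otherwise have counted as in remission. The primary Phase 2b estimand uses data as collected after discontinuation, so it has no equivalent reclassification. The point deserves correction because it concerns a safety stopping rule and the remedy is cheap. It does not by itself call the trial's conclusions into question.

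**What to change.** Reconcile Protocol Sections 6.6.1, 7.1.4, 7.2 and Appendix 10 so that one list governs stopping for liver results. One way is to delete the i.e. text in 6.6.1 and point only to the agreed list. Section 7.1.4 belongs in the exercise because it names laboratory abnormalities of concern as AESIs in general, while 7.2 ties AESI reporting to its narrower stop list. The thresholds, the spacing and the wording on injury or failure are for the sponsor's clinical and safety leads; this review takes no position on them.

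The cost is protocol wording, in an amendment or a clarification letter. The Maintenance SAP (Section 1) records that the Maintenance Study ended early, with last doses by 11 September 2021. For data already collected, the useful step is therefore a sentence in the study report saying which rule sites were told to apply, with any liver-related discontinuations identified against it.
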